- If the participant misses more than 2 consecutive doses of the IMP (see [Section 7.1.2](#)).
- Systemic hypersensitivity reaction including anaphylaxis related or suspected to be related to ice cube provocation test. In the participants who experienced such reaction no further ice cube provocation test should be done during the study.

See the SoA ([Section 1.3](#)) for data to be collected at the time of intervention discontinuation and follow-up and for any further evaluations that need to be completed.

Any abnormal laboratory value or ECG parameter will be immediately rechecked for confirmation within a reasonable timeframe as assessed by the Investigator before making a decision of definitive discontinuation of the IMP for the concerned participant.

If a clinically significant ECG finding is identified (including, but not limited to changes from baseline in QT interval corrected using [Bazett's formula {QTcB} or Fridericia's formula {QTcF}]) at screening, the Investigator or qualified designee will determine if the participant is eligible for the study. This review of the ECG printed at the time of collection must be documented. Any new clinically relevant finding should be reported as an AE.

Handling of participants after definitive intervention discontinuation

Participants will be followed-up according to the study procedures specified in this protocol up to the scheduled date of study completion, or up to recovery or stabilization of any AE to be followed-up as specified in this protocol, whichever comes last.

Participants who discontinue the study intervention prematurely (prior to completing the 24-week treatment period) will perform, as soon as possible, the early treatment discontinuation Visit with all assessments normally planned for the EOT visit (Visit 4), to assure a complete clinical assessment in close temporal proximity to the premature termination of study treatment is available.

In addition, and to allow assessment of participant outcomes over the stipulated study period, participants will be asked and encouraged to complete all remaining study treatment visits and participate in safety follow-up according to the visit schedule with a ± 3 day window. Under exceptional circumstances when a participant cannot come to the study center for a scheduled visit, a phone contact can be made. During the phone contact, at least information about AEs, concomitant medication and status of urticaria should be collected.

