8.3.1 Time period and frequency for collecting AE and SAE information

All AEs, serious or nonserious, will be collected from the signing of the ICF until the EOS Visit at the time points specified in the SoA ([Section 1.3](#)).

All SAEs and AESIs will be recorded and reported to the Sponsor or designee immediately and under no circumstance should this exceed 24 hours, as indicated in Appendix 3 ([Section 10.3](#)). The Investigator will submit any updated SAE/AESI data to the Sponsor within 24 hours of it being available.

Investigators are not obligated to actively seek AEs or SAEs after conclusion of study participation. However, if the Investigator learns of any SAE, including a death, at any time after a participant has been discharged from the study, and he/she considers the event to be reasonably related to the study intervention or study participation, the Investigator must promptly notify the Sponsor.

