4 STATISTICAL ANALYSES

4.1 GENERAL CONSIDERATIONS

This SAP provides a comprehensive and detailed description of strategy and statistical techniques for the summary and analysis of EFC16720.

In general, continuous data will be summarized using the number of observations available, mean, standard deviation (SD), median, minimum, and maximum. Categorical and ordinal data will be summarized using the count and percentage of participants.

The baseline value of efficacy parameters is defined as the last available value up to randomization date and prior to the first dose of study intervention unless otherwise specified. The baseline value of the other parameters is defined as the last available value prior to the first dose of investigational medicinal product (IMP) if the participant is treated, or the last available value up to randomization date if the participant is not exposed to IMP.

Observation period

The observation period will be divided into 4 segments:

- The **pre-treatment period** is defined as the period up to first IMP administration.
- The **treatment-emergent (TE) period** is defined as the period from the first IMP administration to the last IMP administration + 98 days. The treatment-emergent period includes the following 2 periods:
 - The **on-treatment period** is defined as the period from the first IMP administration to the last administration of the IMP + 14 days
 - The **residual treatment period** is defined as the period from the end of the on-treatment period to the end of the treatment-emergent period.
- The **post-treatment period** is defined as the period from the end of the treatment-emergent period.

The on-study period is defined as the time from start of intervention until the end of the study defined as the status date collected on e-CRF page “Completion of End of Study”.

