Analysis of all adverse events

The overview of TEAE with the details below will be generated:

- Any TEAE
- Any severe TEAE
- Any treatment emergent SAE
- TEAE leading to death
- Any TEAE leading to permanent intervention discontinuation
- Any treatment emergent AESI
- Any treatment emergent other AE of interest grouping
- Any TEAE related to IMP

The AE summaries of **Table 6** will be generated with number (%) of participants experiencing at least one event.

Table 6 - Analyses of adverse events

Type of AE	MedDRA levels
All TEAE	Primary SOC, HLGT, HLT and PT
	Primary SOC and PT
	PT
	Primary and secondary SOC, HLGT, HLT and PT
Common TEAE $\geq 5\%$ in any group)	Primary SOC and PT
TEAE related to IMP as per Investigator's judgment	Primary SOC, HLGT, HLT and PT
	Primary SOC and PT
TEAE by maximal intensity	Primary SOC and PT
Treatment emergent SAE	Primary SOC, HLGT, HLT and PT
	Primary SOC and PT
Treatment emergent SAE related to IMP as per Investigator's judgment	Primary SOC, HLGT, HLT and PT
TEAE leading to permanent intervention discontinuation	Primary SOC, HLGT, HLT and PT
	Primary SOC and PT
TEAE leading to death (death as an outcome of the AE as reported by the Investigator in the AE page)	Primary SOC, HLGT, HLT and PT
Pretreatment AE	Overview ^a
	Primary SOC and PT

^a Will include the following AE categories: any AEs, any serious AEs, any AEs leading to death, any AEs leading to permanent intervention discontinuation

In addition, the exposure adjusted incidence rate of TEAEs by primary SOC and PT will be generated, showing the number of participants with at least one TEAE per 100 patient-years. For participants with an event, patient-years will be calculated up to the first event, and for participants without an event, patient-years will correspond to the length of the TE period.

Risk differences (constructed using the Miettinen and Nurminen method) and hazard ratios (Cox proportional hazards model) for dupilumab versus placebo with corresponding 95% CIs will be provided for the common TEAEs (PT \geq 5% in any intervention group). Participants without an event will be censored at the end of the treatment-emergent period in the Cox model. Forest plots will also be presented.

Analysis of deaths

In addition to the analyses of deaths included in [Table 5](#) the number (%) of participants in the following categories will be provided:

- Deaths during the treatment-emergent and post-treatment periods

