4.9 INTERIM ANALYSES

No interim analysis is planned.

A primary database lock will be performed when all randomized participants in this study have completed their 24-week treatment phase. Analysis will be based on all data collected up to the database cut-off date and will be considered as the final analyses in the CSR.

The database will be updated at the end of the study for all participants to include the post-treatment follow-up information and updates for the events previously ongoing at the time of the primary lock. Additional data between this database lock and last participant completing last visit will be summarized in a CSR addendum.

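### SAP 4.7.2 runs time at risk for event-free participants to last dose plus 98 days, with no cap at study exit, death or data cut-off

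*SAP*

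**What the plan says.** SAP 4.7.2 computes the exposure-adjusted rate with time to first event for participants who have one; "for participants without an event, patient-years will correspond to the length of the TE period". For the hazard ratios it adds: "Participants without an event will be censored at the end of the treatment-emergent period in the Cox model".

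SAP 4.1 fixes the treatment-emergent (TE) period by dosing dates only: it "is defined as the period from the first IMP administration to the last IMP administration + 98 days". The same section defines a second interval that does end with observation ("The on-study period is defined as the time from start of intervention until the end of the study", taken from a status date on the case report form), but 4.7.2 does not use it.

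Two other rules limit what is observed. Protocol 8.3.1 says: "All AEs, serious or nonserious, will be collected from the signing of the ICF until the EOS Visit". SAP 4.9 says: "A primary database lock will be performed when all randomized participants in this study have completed their 24-week treatment phase". It continues: "Analysis will be based on all data collected up to the database cut-off date". Later data go to an addendum.

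For participants who stop treatment early, Protocol 7.1.1 plans continued follow-up: "participants will be asked and encouraged to complete all remaining study treatment visits and participate in safety follow-up according to the visit schedule".

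**The concern.** In a rate, events and time at risk must stop together. Here the numerator stops when routine collection stops or the data are cut, while the denominator runs on to a date computed from the last dose. The extra time can contain no recorded event, so within each arm the error has one direction: the rate is too low.

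Three kinds of participant are affected:

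- those not yet at Week 36 when the primary database is cut;
- those who leave the study or die within 98 days of their last dose;
- completers whose final visit falls early in the Week 36 ± 7 day window.

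Someone who stops treatment but stays under observation for the full 98 days is counted correctly once follow-up is complete.

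At stake are the exposure-adjusted rates and hazard ratios that SAP 4.7.2 plans. The rates for adverse events of special interest (AESIs) and other groupings would follow if the same rule is reused there. The SAP gives no denominator rule for those groupings, so that part is an inference.

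**Working it through.** **Reproducing the plan's calendar.** The last planned dose is at Week 22 (Protocol 6.1.1), which is Day 1 + 22 × 7 = Day 155. Adding 98 gives Day 253, exactly the Week 36 target day in the SAP's visit-window tables. For a completer seen on schedule, the rule and the observation period agree.

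**Single participants.**
- At Week 24 (Day 169) when the data are cut: 253 − 169 = 84 days unobserved, 84/253 = 33.2%.
- Final visit on Day 246: 253 − 246 = 7 days, 2.8%.
- Leaves on the day of the last dose: up to 98 days.

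**Trial level, effect of the lock alone.** Assume uniform accrual over A weeks, a cut-off g weeks after the last Week 24 visit, and everyone event-free. The planned TE length is 22 + 14 = 36 weeks, and the mean unobserved time is (12 − g)²/(2A) weeks.

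| A (weeks) | g = 0 | g = 6 | g = 12 |
|---|---|---|---|
| 66 | 144/132 = 1.09 weeks; 3.0% | 0.8% | 0 |
| 104 | 144/208 = 0.69 weeks; 1.9% | 0.5% | 0 |
| 156 | 144/312 = 0.46 weeks; 1.3% | 0.3% | 0 |

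The documents do not give A. The 66 weeks is a lower bound for g = 0, assuming that the cut-off is the lock date. The first randomization was on 04 January 2021 and the SAP rests on an amendment of 27 September 2022, 631 days or 90.1 weeks later. The SAP precedes the lock (Protocol 9.4), and 90.1 − 24 = 66.1. For other g the bound is 66.1 − g.

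**Adding study exit.** The documents give no study-exit rate. As a scenario, let 10% stop treatment, with the last dose uniform over Weeks 0 to 22 (mean 11). Mean TE length is 0.9 × 36 + 0.1 × (11 + 14) = 34.9 weeks.
- All stay in the study: 2.9% at the lock (A = 66, g = 0) and 0 in the final database.
- All leave 2 weeks after the last dose, each losing 14 − 2 = 12 weeks: final database 0.1 × 12/34.9 = 3.4%. At the lock with A = 66, g = 0: (0.9 × 1.09 + 1.2)/34.9 = 6.2%. With A = 104: (0.9 × 0.69 + 1.2)/34.9 = 5.2%.

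**What that does to a rate.** Take a constant hazard with 25% event probability by Week 36. The true rate is −ln(0.75)/36 × 52.18 × 100 = 41.7 per 100 patient-years. Simulated understatement at the lock (A = 66, g = 0) is 2.6% if all stay and 6.1% if all leave, giving 41.7 × 0.974 = 40.6 and 41.7 × 0.939 = 39.2.

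**Comparison between arms.** With 10% exit in both arms the rate ratio is unchanged. With an assumed 5% versus 15%, all leaving, final database:
- 5% arm: 0.05 × 12/(0.95 × 36 + 0.05 × 25) = 0.6/35.45 = 1.7%.
- 15% arm: 0.15 × 12/(0.85 × 36 + 0.15 × 25) = 1.8/34.35 = 5.2%.
- Rate ratio multiplied by 0.983/0.948 = 1.04, or 0.96 if the arms are swapped.

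Cox models fitted to simulated data from these scenarios show the same: no change at 10% versus 10%, and a shift of about 4% at 5% versus 15%, for event probabilities of 5%, 25% and 50%.

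**For scale.** A rate based on 10 participants with an event has an exact Poisson 95% interval of 0.48 to 1.84 times the estimate. The effect of death was not quantified.

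**The case against.** The strongest reply is that SAP 4.9 already limits the analysis to data up to the cut-off, and that a sensible programmer would end follow-up time there too. That reading is open, and on it the lock effect disappears. But 4.9 states no patient-years rule. A TE length needs only dosing dates, so a program can obey 4.1, 4.7.2 and 4.9 together and still count time beyond the cut-off. Nor does 4.9 address study exit or death.

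A second reply is that exit will be rare. Protocol 7.2 expects withdrawal to be uncommon, and Protocol 7.1.1 plans continued follow-up. This stands and limits the size. A reader might take the 10% drop-out in SAP section 2 as the share leaving the study. The documents do not support that: it is a sample-size assumption, and the scenario in which all of them leave two weeks after the last dose is near the worst case.

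A third reply concerns the numerator. Protocol 8.3.1 also asks investigators to report related serious events learned of after discharge, so collection does not stop completely at the final visit. This stands too: capping event-free time alone would leave such events in the numerator without matching time at risk. The fix must deal with both.

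**Conclusion.** The rule as written counts unobserved event-free time, and no other text corrects it. Exposure-adjusted rates can be understated by 0% to about 6% in the scenarios above. These assume uniform accrual of at least 66 weeks, a chosen cut-off date and chosen exit rates. Several of them give zero.

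Two stronger readings are tempting and unsupported. One is that the safety rates will be biased: that depends on how the cut-off is applied and how many participants leave, which the documents do not fix. The other is that the comparison between arms is materially distorted: equal exit leaves it essentially unchanged, and a threefold exit imbalance moves the hazard ratio by about 4%, which is small beside the sampling error with 39 per arm.

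Counts, percentages and risk differences do not use this time and are unaffected. SAP 4.7 makes the safety analysis descriptive, without testing. The correction is minor but worth making, because two programmers could obtain different rates from the present text.

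**What to change.** Add to SAP 4.7.2, for the exposure-adjusted rates and the Cox model:

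- Time at risk for a participant without an event ends at the earliest of last dose plus 98 days, the end-of-study status date already defined in SAP 4.1, death, and the data cut-off date.
- An event counts in these two analyses only if its onset is on or before that date. A participant whose only event comes later is censored at that date. TEAEs reported later stay in the count and percentage tables and are listed.
- The same rule applies to the rates and hazard ratios for AESIs and other groupings, and to Kaplan-Meier estimates if they are produced.

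Leave the TE definition in SAP 4.1 unchanged, since it also classifies adverse events, deaths and laboratory abnormalities.

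The cost is a few lines of SAP text and a standard programming step. No new data are needed and no event is reclassified.

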Systemic hypersensitivity has been established as an important identified risk with dupilumab. As protein therapeutics, all mAbs are potentially immunogenic. Rare serious and systemic hypersensitivity reactions have been observed in the dupilumab program including serum sickness/serum sickness-like reaction in the adult AD program and anaphylaxis related to dupilumab in the adult asthma clinical studies.

The important potential risk for dupilumab is “eosinophilia associated with clinical symptoms in asthma patients.” The observed increase in eosinophil count is transient, which is consistent with

the current understanding of the mechanism of action of dupilumab. In dupilumab asthma studies, a small number of patients with asthma experienced serious systemic eosinophilia presenting with clinical features of eosinophilic pneumonia or vasculitis consistent with eosinophilic granulomatosis with polyangiitis, conditions which are often treated with systemic corticosteroids (SCS) therapy. These events have been seen in other drug development programs for severe asthma and usually, but not always, have been associated with the reduction of oral corticosteroid therapy suggesting possible unmasking of these conditions with tapering of corticosteroids during dupilumab therapy. The association of dupilumab treatment and these events has not been established. Health care providers should be alert to eosinophilia associated with vasculitis rash, worsening of pulmonary symptoms, pulmonary infiltrate, cardiac complications, and/or neuropathy presenting in their patients, especially upon reduction of SCS.

Patients with known helminth infections were excluded from participation in clinical studies, therefore it is not known if dupilumab will influence the immune response against helminth infections. Consequently, patients with pre-existing helminth infections should be treated for their helminth infection before initiating therapy with dupilumab.

The common ADR across all indications is injection site reaction. Other potential risks based on the safety profile in particular indications are discussed in the IB.

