The clinical picture of a participant at the time of study visits may not be totally representative of the actual current disease status due to symptom fluctuation that is dependent upon the contact with the triggering temperature. Therefore, the participants will rate the disease activity using the ColdUAS questionnaire in an e-diary. On a daily basis, participants will report their skin reactions (wheals and swelling), skin sensations (itching, burning, pain or feeling hot), avoidance behavior and trigger exposure, and overall symptoms severity. Cold Urticaria Activity Score will provide important supportive information on clinical improvement of the participants on a daily basis. Since skin reactions, skin sensations and behavioral avoidance to trigger vary from one day to another, ColdUAS will be assessed on a daily basis.

Participants with primary inducible ColdU are at risk of developing systemic hypersensitivity reactions including anaphylaxis after exposure to cold triggers. Such systemic reactions are mainly described as provoked by aquatic activities (eg, swimming in cold water) when the whole body, or a large proportion of it, was in contact with cold. Systemic hypersensitivity events will be documented via adverse event of special interest (AESI)/serious adverse event (SAE) reporting, and information about corrective treatment will be collected.

To get a complete picture of the disease, it is important to assess disease control over the course of treatment in addition to urticaria symptom assessment. Patients are best positioned to accurately assess this control, as they experience and feel it. They will self-assess their ColdU control using the urticaria control test (UCT), a well-developed and validated instrument in chronic urticaria patients (25).

Lastly, patients with primary acquired chronic inducible ColdU experience substantial HRQoL impairment. Therefore, the DLQI, a dermatology-specific instrument designed to assess HRQoL in adults ≥ 16 years old (26) with dermatologic conditions, and the corresponding Children's Dermatology Life Quality Index (CDLQI) for adolescents aged ≥ 12 years to < 16 years old will be used, in addition to the newly developed disease-specific Cold Urticaria Quality of Life (ColdU-QoL) questionnaire..

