5.1 INCLUSION CRITERIA

Participants are eligible to be included in the study only if all of the following criteria apply:

Age

I 01. Participant must be ≥ 12 years to 80 years (or the minimum legal age for adolescents in the country of the investigational site) of age inclusive at the time of signing the informed consent. For those countries where local regulations do not permit enrollment of adolescents (≥ 12 years to <18 years of age), the recruitment will be restricted to those who are ≥ 18 years of age.

Type of participant and disease characteristics

I 02. Participants who have a diagnosis of primary acquired chronic inducible ColdU defined as recurrence of itchy wheals and/or angioedema due to cold for longer than 6 weeks prior to screening visit (Visit 1).

I 03. Participants with positive ice cube provocation test, ie, presenting at least a confluent hive/wheal on the exposed skin area, at the screening visit (Visit 1) and randomization visit (Visit 2).

I 04. Participants meeting at least 1 of the following criteria despite regular/daily or as needed use of H1-antihistamine:

- Urticaria Control Test (UCT) (4-item) <12 at the screening visit (Visit 1) and randomization visit (Visit 2)
- Within 6 months prior to the screening visit, documented medical history of cold exposure triggered anaphylaxis or oropharyngeal edema
- Within 6 months prior to the screening visit, documented medical history of cold exposure triggered urticaria requiring emergency medical care visit or treatment with epinephrine.

I 05. Participants who are using a study-defined H1-antihistamine regularly/daily or as needed for primary acquired chronic inducible ColdU (see [Section 6.1.2](#) for the list of antihistamines allowed for the study). Regular/daily use is defined as H1-antihistamine intake for at least 4 days per week for at least 1 month prior to screening visit (Visit 1).

Note: The participants who take H1-antihistamine regularly/daily should have the dose stable for at least 5 consecutive days prior to screening visit (Visit 1). The participants who

take H1-antihistamine as needed should not take H1-antihitamine for at least 5 consecutive days prior to screening visit (Visit 1).

Weight

I 06. Body weight \geq 30 kg.

Sex

I 07. Male or Female

Contraceptive use by women should be consistent with local regulations regarding the methods of contraception for those participating in clinical studies.

a) Female participants

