A serious feature of ColdU is anaphylaxis. Thirty-five percent to 70% of patients with chronic inducible ColdU have experienced systemic reactions including anaphylaxis in severe cases. (6, 37, 38).

Anaphylaxis is defined as a severe, potentially life-threatening systemic hypersensitivity reaction, characterized by being rapid in onset with life-threatening airway, breathing, or circulatory problems that is usually, though not always, associated with skin and mucosal changes.

When the diagnosis of anaphylaxis is made, the basis for having suspected the diagnosis must be documented, using the criteria in Appendix 10 ([Section 10.10](#)), established by the Second Symposium on the Definition and Management of Anaphylaxis (37, 39). Reports of anaphylaxis will be collected as AESIs in the eCRF.

All participants with ColdU and their parents/legal representative/caregiver should be cautioned regarding the risk of anaphylaxis and provided with an epinephrine autoinjector.

The proportion of participants with cold exposure triggered urticaria requiring emergency medical care visit or treatment with epinephrine (after provocation test and/or at home) will be evaluated.

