- Deaths in non-randomized or randomized but not treated participants

Analysis of adverse events of special interest (AESIs) and other AEs of interest

Adverse events of special interest (AESIs) and other AEs of interest will be selected for analyses as indicated in [Table 7](#). Number (%) of participants experiencing at least one event will be provided for each event of interest. Tables will be sorted as indicated in [Table 5](#).

Table 7 - Selections for AESIs and other AEs of interest

AE Grouping	Criteria
AESI	
Anaphylactic reaction	Anaphylactic reaction algorithmic approach (Introductory Guide for Standardised MedDRA Queries (SMQs) Version 18.1): includes anaphylactic reaction narrow SMQ (20000021) terms and programmatic identification of cases based on occurrence of at least two preferred terms meeting the algorithm criteria occurring within 24 hours of each other. The latter cases identified using the algorithm will undergo blinded medical review taking into account the timing of events relative to each other and to IMP administration for final determination of an anaphylactic reaction or not.
Systemic hypersensitivity reactions	SMQ [20000214] hypersensitivity narrow search and [AE corrective treatment/therapy = 'Y' or Action taken with IMP = 'Drug withdrawn' or Action taken with IMP = 'Drug interrupted'] followed by blinded medical review (documented process) for selection of relevant systemic hypersensitivity events
Helminthic infections	CMQ10544 based on HLGT as "Helminthic disorder"
Any severe type of conjunctivitis	CMQ10498 based on PTs (See Section 5.5) ^a and "Severe" ticked in Adverse Events eCRF page
Any severe type of blepharitis	CMQ10497 based on HLGT as "Lid, lash and lacrimal infections, irritations and inflammations" and "Severe" ticked in Adverse Events eCRF page
Keratitis	CMQ10642 based on the following PTs [keratitis, allergic keratitis, ulcerative keratitis, atopic keratoconjunctivitis, herpes ophthalmic, ophthalmic herpes simplex, corneal infection] ^a

AE Grouping	Criteria
Clinically symptomatic eosinophilia (or eosinophilia associated with clinical symptoms) ^b	CMQ10641 based on HLT = Eosinophilic disorders or PT = Eosinophil count increased
Pregnancy of a female patients entered in a study as well as pregnancy occurring in a female partner of a male patient entered in a study with IMP/NIMP	"Pregnancy" or "Partner Pregnancy" checked on the Pregnancy eCRF page as reported by the investigator

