- The exposure adjusted incidence rate by selected SMQ/CMQ and PT showing the number of participants with at least one TEAE per 100 patient-years.

- All TEAEs, by selected SMQ/CMQ including risk differences and hazard ratios with corresponding 95% CIs.
- For each AESI and other selected AE groupings,
 - Number (%) of participants with any specific TEAE
 - Number (%) of participants with any specific serious AE (regardless of treatment emergent status)
 - Number (%) of participants with any specific treatment emergent serious AE
 - Number (%) of participants with any specific AE leading to death
 - Number (%) of participants with any specific TEAE leading to permanent study drug discontinuation
 - Number (%) of participants with any specific TEAE related to IMP reported by investigator
 - Number (%) of participants with any specific TEAE by maximum intensity, corrective treatment, and final outcome
 - Number (%) of participants with any specific TEAE adjusted by the exposure duration
 - Time to onset of first TEAE and cumulative incidence at specified time points (K-M estimates at Week 12 and 24) and K-M plot may be provided to depict the course of onset over time if the number of events is large enough.
 - Number (%) of participants with injection site reactions by the related injection.
 - Number (%) of participants with different number of injection site reactions.
- In addition, AESIs reported by the investigator in eCRF will be summarized separately.

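### The anaphylaxis AESI counts every narrow-SMQ event whatever its trigger, and the AESI risk differences and hazard ratios do not separate cold-triggered from other reactions

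*SAP*

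**What the plan says.** The protocol recognizes two sources of the same kind of event.

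- Disease: "A serious feature of ColdU is anaphylaxis" (Protocol 8.3.7), and "Participants with primary inducible ColdU are at risk of developing systemic hypersensitivity reactions including anaphylaxis after exposure to cold triggers" (Protocol 3.1). Recent cold-triggered anaphylaxis is one of three alternative ways to meet inclusion criterion I 04: "Within 6 months prior to the screening visit, documented medical history of cold exposure triggered anaphylaxis or oropharyngeal edema".
- Drug: "Systemic hypersensitivity has been established as an important identified risk with dupilumab" (Protocol 2.3.2).

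Both go into the same reporting stream. In the paragraph on reactions to cold, Protocol 3.1 states: "Systemic hypersensitivity events will be documented via adverse event of special interest (AESI)/serious adverse event (SAE) reporting". Protocol 8.3.7 adds, without distinguishing cause: "Reports of anaphylaxis will be collected as AESIs in the eCRF".

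In the SAP, the Table 7 definition of anaphylactic reaction "includes anaphylactic reaction narrow SMQ (20000021) terms and programmatic identification of cases". Only the algorithm-identified cases go to blinded medical review, which considers timing relative to IMP and decides whether the case is anaphylaxis. Systemic hypersensitivity is a narrow SMQ search plus corrective treatment or an IMP action, followed by a blinded review that keeps relevant events; relevance is not defined. The between-arm output in SAP 4.7.2 is "All TEAEs, by selected SMQ/CMQ including risk differences and hazard ratios with corresponding 95% CIs". For each AESI the SAP also plans a count of participants with events the investigator relates to IMP.

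**The concern.** The estimated difference in anaphylaxis between arms is meant to inform a known drug risk. In this population the same code can also record the disease responding to cold, which the drug is intended to reduce. The two contributions have opposite signs. A pooled risk difference near zero, or in favor of dupilumab, is then compatible both with no drug-related reactions and with drug-related reactions cancelled by fewer cold-triggered ones. The AESI comparison cannot tell a reader which of these it shows.

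**Working it through.** **Plan figures.** No stated figure is in dispute. The 39 per arm (SAP section 2) serves only as a denominator. Its derivation cannot be reproduced because the response rates are blacked out.

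**Where trigger is considered.**

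| Route into the AESI | Review before counting | Rule on trigger |
|---|---|---|
| Anaphylaxis, narrow SMQ | None stated | None |
| Anaphylaxis, algorithm | Blinded; looks at timing to IMP | None stated; decides anaphylaxis or not |
| Systemic hypersensitivity | Blinded; keeps relevant events | Criteria not given |

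Protocol 7.1.1 requires permanent withdrawal of IMP after a systemic reaction to the ice cube test. Such a case, if coded in the hypersensitivity SMQ, passes the action part of that filter. The treatment-emergent period runs to last dose + 98 days (SAP 4.1). With a last dose at Week 22 (Day 22 × 7 + 1 = 155), it ends on Day 253, the Week 36 target day. A reaction to the off-drug Week 36 provocation test can therefore also be counted.

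**Break-even.** Let c be the placebo risk of a cold-triggered event, e the relative reduction by dupilumab and q the risk of a drug-caused event. The documents give none of these; all are assumptions, and independence is assumed. Participants count once.

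- Placebo risk: c
- Dupilumab risk: 1 - (1 - c(1 - e))(1 - q)
- The pooled difference is zero when q = 1 - (1 - c)/(1 - c(1 - e))

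Example: c = 5%, e = 50% gives 1 - 0.95/0.975 = 2.56%.

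| c | e = 25% | e = 50% | e = 75% |
|---|---|---|---|
| 2% | 0.51% | 1.01% | 1.51% |
| 5% | 1.30% | 2.56% | 3.80% |
| 10% | 2.70% | 5.26% | 7.69% |
| 20% | 5.88% | 11.11% | 15.79% |

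Any smaller q gives a pooled difference in favor of dupilumab.

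**Precision at 39 per arm.** Differences are dupilumab minus placebo, in percentage points, with Miettinen-Nurminen 95% intervals. The SAP names that method for common TEAEs; it is assumed here for the AESI groupings. Counts are illustrative, with each event in a different participant and no drug-caused events on placebo.

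| Cold-triggered, placebo v dupilumab | Drug-caused, dupilumab | Pooled | Drug-caused only | Cold-triggered only |
|---|---|---|---|---|
| 2 v 1 | 1 | 0.0 (-12.6 to 12.6) | +2.6 (-6.6 to 13.3) | -2.6 (-14.8 to 8.8) |
| 4 v 2 | 1 | -2.6 (-17.2 to 11.8) | +2.6 (-6.6 to 13.3) | -5.1 (-19.4 to 8.2) |
| 4 v 2 | 2 | 0.0 (-15.1 to 15.1) | +5.1 (-4.2 to 17.0) | -5.1 (-19.4 to 8.2) |
| 8 v 4 | 4 | 0.0 (-18.4 to 18.4) | +10.3 (0.7 to 23.7) | -10.3 (-27.1 to 6.3) |

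Third row: pooled 4/39 - 4/39 = 0; drug-caused 2/39 - 0/39 = 5.1 points. The offset is arithmetically easy to produce. Except with 4 v 0 events, the interval for the drug-caused class also includes zero.

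**The case against.** A reader might infer that an effective drug could hide its own hypersensitivity risk altogether. The documents do not support that.

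- The SAP plans an IMP-related count for every AESI, so 2 v 0 correctly attributed reactions would appear as 2 v 0. Investigators are blinded, and Protocol 10.3.3 tells them to weigh underlying disease and timing.
- Investigator-reported AESIs are summarized separately.
- Cold-triggered urticaria needing emergency care or epinephrine is its own secondary endpoint (SAP 4.4.2).
- Protocol 8.3.6 limits which cold urticaria episodes become AEs.

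A reader might also infer that the systemic hypersensitivity review leaves cold-triggered events in. It may remove them; its criteria are simply not in these documents. Nor is a safety objective left unanswered: the stated endpoint is the percentage of participants with TEAEs or SAEs, and SAP 4.7 makes the analysis descriptive, without testing. Finally, the 35% to 70% with systemic reactions is disease history, not an on-study rate, and exclusion E 02 covers systemic reactors to the ice cube test at screening and randomization.

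All of this stands and limits the point. It does not close the gap. The IMP-related count is investigator opinion, treats missing relatedness as related, and has no stated risk difference. The emergency-care endpoint is not linked to the AESI tables. None of these measures gives narrow-SMQ anaphylaxis a trigger review or splits the comparison.

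**Conclusion.** The concern holds in a limited form. For narrow-SMQ anaphylaxis, the plan as written counts events regardless of trigger and compares the arms on that total. For algorithm-found anaphylaxis and systemic hypersensitivity, mixing is possible but not shown. Whether a material offset would occur depends on assumed rates: a drug-caused risk between 0.5% and 15.8% is cancelled over the range examined. With 39 per arm, a split by trigger would be descriptive. Its value is that it stops a mixed estimate from being read as reassurance and puts the relevant cases in front of the reviewer.

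**What to change.** In SAP Table 7 and 4.7.2, before database lock:

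1. Extend the planned blinded medical review to the narrow-SMQ anaphylaxis cases.
2. State what makes a systemic hypersensitivity event relevant.
3. Have the review assign each case to cold-triggered (provocation test or environmental), not cold-triggered, or uncertain.
4. Report counts, exposure-adjusted rates and risk differences for each class beside the pooled total, and show the not-cold-triggered result with and without the uncertain cases.
5. Apply the same split to the ADA association analysis (SAP 4.8.2.1) if it is done.

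The uncertain class matters. If dupilumab works, misclassified cold reactions will be more frequent on placebo, and moving them into the not-cold-triggered class biases that class in favor of dupilumab. In the 4 v 2 plus 2 example, if half the cold-triggered events were uncertain and were moved there, the difference would fall from 2/39 - 0/39 = +5.1 points to 3/39 - 2/39 = +2.6 points.

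The cost is SAP wording, some extra blinded review and a few table rows; nothing planned is removed and the sample size is unaffected. Counts per class will be small. The documents show no dedicated AE field for trigger, so the review would have to rely on event narratives, timing to the provocation test and IMP, and the daily diary record of cold exposure.
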